## **11. STATISTICAL METHODS**

### **11.1 Hypothesis**

Physical Function [AU]

H0: The use of cryotherapy with intermittent dynamic compression has no positive effect on the physical functions of patients after a total knee arthroplasty.

H1: The use of cryotherapy with intermittent dynamic compression has a positive effect on the physical functions of patients after a total knee arthroplasty.

Patient satisfaction [cm]

H0: The use of cryotherapy with intermittent dynamic compression has no positive effect on patient satisfaction of patients after a total knee arthroplasty.

H1: The use of cryotherapy with intermittent dynamic compression has a positive effect on patient satisfaction of patients after a total knee arthroplasty.

Joint circumference [mm]

H0: The joint circumference is not reduced by cryotherapy with intermittent dynamic compression compared to the control group during a hospital stay.

H1: The joint circumference is reduced by cryotherapy with intermittent dynamic compression compared to the control group during a hospital stay.

Skin temperature [C°]

H0: The skin temperature is not reduced by cryotherapy with intermittent dynamic compression compared to the control group during a hospital stay.

H1: The skin temperature is reduced by cryotherapy with intermittent dynamic compression compared to the control group during a hospital stay.

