Intervention:	
The Game Ready GR PRO 2.1 is a certified product that complies with European regulations, directives and standards.
 
The system can administer ice-free cold treatment and intermittent pneumatic compression treatment, providing healthcare professionals with options for different patients, procedures, injuries and rehabilitation stages.
 
The following intervention is performed according to the manufacturer's protocol for patients with primary total knee arthroplasty: 48 hours after the operation starts the Game Ready Intervention, if tolerable, with little compression (level 1 = 5-15 mmHg) and cooling at the coldest level tolerable by the participant (corresponds to program 2). The cooling should be perceived as "pleasant" by the participant. The intervention lasts one hour, of which 30 minutes are on and 30 minutes off cycles. The on cycle includes the duration of the intervention (cooling and compression), while the off cycles include the rest period. After 60 minutes, the device is removed. If compression is not tolerated, it can also be omitted (corresponds to program 1). The intervention is performed twice a day for the first four days after surgery. The coldest tolerable temperature level is determined anew with each treatment. The compression level can be increased depending on the participant. Medium compression may only be applied from the second day onwards (corresponds to programme 3).

Control intervention (if applicable):	
In order to obtain high-quality study results, the test subjects are exposed to only one experimental condition at a time. There are two groups. In order to maintain the quality of the study, a randomized controlled trial design will be chosen. The division into the groups is randomized. The data collected in this way is pooled by outcome or group.
 
The control group will receive ordinary physiotherapy treatment, without Game Ready application.

Number of subjects with rationale:	
n=28 (14 per group) G-Power analysis: effect size at 0.8

Duration of the investigation:	
May 2022 – December 2024

Investigation schedule:	
May 2022- subject –In (planned) June 2023- subject –Out (planned)

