#### Aim of the study

In this project, the effect of repeated cold application with dynamic compression with the Game Ready and a control group will be investigated. The influence of these interventions and their effects will be investigated after a primary total knee endoprosthesis operation during the hospital stay. The change in the following parameters is examined: questionnaire on everyday functions and patient satisfaction, joint circumference in mm, range of motion in degrees, skin temperature in C°, morphine consumption per day, pain perception with the VAS, the 10-meter walk test, timed-up-and-go and the length of the days of stay.

The aim is to determine the effects of cold application with dynamic compression in order to be able to make recommendations. The current scientific knowledge requires further studies to substantiate or refute effects that have already been established.

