## 6. CLINICAL INVESTIGATION DESIGN

### 6.1 General clinical investigation design and justification of design

Randomized, controlled trial

It is a clinical investigation concerning medical devices (MD), Category according to Art 6 ClinO-MD (A1), whereby a CE-certified medical device is tested in the intervention group.

The group size of the participants is n=28 people (per group n=14 people). The group assignment is randomized.

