## 11.2 Determination of Sample Size

A power analysis was performed using the G\*Power App (Düsseldorf, North Rhine-Westphalia, DEU), where a minimum number of 28 subjects was deemed necessary to ensure the statistical power (0.95) to detect a parameter difference at the 5% significance level. The figure below shows the G-Power calculation that was used to determine the sample size.

*Figure 4: Sample Size Calculation*

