### 11.4.2 Primary Analysis

The statistical data analysis will be carried out by [name] after completion of the data collection of the entire project.

Repeated measures analysis of variance (MANOVA) 2

factors:

Factor 1: Intervention (Game Ready vs. Control Intervention)

Factor 2: Time (baseline, 4th postoperative day and 6 weeks)

The significance level is set to  $p < 0.05$ . Statistical data analysis is carried out with SPSS.

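### Section 11.1 asks directional questions about the hospital stay, but the planned F-test over three visits has no direction and names no deciding Day-4 contrast, estimate or interval

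*Combined protocol and SAP*

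**What the plan says.** Section 11.1 gives nine pairs of hypotheses. Each H1 names a benefit, and each H0 covers everything else. For swelling, the pair is "H0: The joint circumference is not reduced by cryotherapy with intermittent dynamic compression compared to the control group during a hospital stay" and "H1: The joint circumference is reduced by cryotherapy with intermittent dynamic compression compared to the control group during a hospital stay". Seven of the nine pairs (circumference, skin temperature, morphine, pain, 10-metre walk, Timed-Up-and-Go, length of stay) are tied to the hospital stay. Physical function and patient satisfaction are not.

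Section 5.1 calls the preoperative measurement the baseline, the 4th postoperative day the primary endpoint, and the 6-week measurement follow-up.

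Section 11.4.2 names one analysis: "Repeated measures analysis of variance (MANOVA) 2" factors, intervention and time, with time at baseline, Day 4 and 6 weeks, and significance at p<0.05. It does not say whether the group main effect or the group-by-time interaction decides. It names no contrast, estimate or interval, and does not say how a non-significant result is to be read. The synopsis adds a Bonferroni correction without saying to how many comparisons it applies.

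On size, section 6.1 states "The group size of the participants is n=28 people (per group n=14 people"), section 11.2 speaks of power 0.95 "to detect a parameter difference at the 5% significance level", and the synopsis gives "G-Power analysis: effect size at 0.8".

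**The concern.** The question, the endpoint and the test do not line up.

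- **Direction.** Harm and no effect both sit inside each H0. An F-test rejects for a difference either way, and the plan does not link a significant F to a sign.
- **Time.** An interaction over three visits has 2 degrees of freedom. A difference that appears only at 6 weeks can make it significant, although the declared endpoint is Day 4 and most hypotheses end with the hospital stay. The group main effect averages over all three visits, including a baseline measured before any treatment, so a Day-4 effect is diluted.
- **Null results.** Without an estimate and interval, p>0.05 does not tell the reader which benefits are ruled out and which remain open.

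The stated aim is to determine effects so that recommendations can be made. Two analysts could follow section 11.4.2 faithfully, look at different effects, and reach different conclusions for the same outcome.

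**Working it through.** **Inputs.** 14 per group (section 6.1); effect size 0.8 (synopsis), read here as a standardised mean difference because the metric is not stated; two-sided alpha 0.05 (section 11.2 gives 5%, sidedness not stated); three visits (section 11.4.2). The correlation between visits is not in the documents, so 0.3, 0.5 and 0.7 are assumed, with equal variances and sphericity. All figures are in SD units for one outcome, before any Bonferroni correction.

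**The plan's own figure.** For a plain two-group t-test at d = 0.8 and 14 per group, the noncentrality is 0.8 × √(14/2) = 2.117 and two-sided power is 0.53, not 0.95. Power of 0.95 would need 42 per group. Totals near 28 do arise from a repeated-measures calculation with inputs the text does not give: an interaction with f = 0.25, three visits and correlation 0.7 gives 28; f = 0.4 with correlation 0.3 gives 26. The G\*Power figure is not shown, so whether 28 is reproduced cannot be settled, and this point does not depend on it.

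**Precision at Day 4.**

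- Unadjusted half-width: t(0.975, 26) × √(2/14) = 2.056 × 0.378 = 0.777 SD.
- Adjusted for baseline, approximately: 0.777 × √(1 − ρ²) = 0.74, 0.67 and 0.55 SD at ρ = 0.3, 0.5 and 0.7. Spending one further degree of freedom on the baseline term changes the last to 0.56.
- With 12 completers per group, unadjusted: t(0.975, 22) × √(2/12) = 0.85 SD. Section 11.4.1 analyses complete data only, so 14 per group is an upper limit.

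**Power of the candidate tests when the groups differ by 0.8 SD on Day 4 and at no other visit.** The group deviations from the common mean are ±0.4 on Day 4 and 0 otherwise.

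- Group main effect: λ = 28 × 3 × (0.4/3)² / (1 + 2ρ) = 1.493 / (1 + 2ρ), tested on F(1, 26).
- Group-by-time interaction: λ = 28 × 0.4² × (2/3) / (1 − ρ) = 2.987 / (1 − ρ), tested on F(2, 52).
- Baseline-adjusted Day-4 contrast: noncentrality 0.8 × √7 / √(1 − ρ²), tested on t(25).

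| ρ (assumed) | Group main effect | Interaction, 2 df | Adjusted Day-4 contrast |
|---|---|---|---|
| 0.3 | 0.15 | 0.42 | 0.57 |
| 0.5 | 0.13 | 0.56 | 0.65 |
| 0.7 | 0.12 | 0.79 | 0.81 |

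**Which visit drives the F.** The interaction formula treats the three visits alike. A 0.8 SD difference at 6 weeks only, with none on Day 4, gives the same λ and the same chance of significance, 0.42 to 0.79. The λ values depend on squared deviations, so they are also unchanged if the sign is reversed.

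**The case against.** The strongest reply is that H1 already names the direction. Any competent analyst would look at the means, and nothing in the plan tells them to ignore the sign. That largely stands. For a single contrast, a two-sided 5% test with benefit claimed only in the favourable direction is conservative for the directional H1: the chance of a significant result in the wrong direction is 2.5% if the true effect is zero and 0.06% if the true benefit is 0.5 SD. The mismatch of direction is a gap in the written rule and does not inflate error. The reply does not cover the choice between main effect and interaction, or the influence of the 6-week visit.

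Three stronger readings are tempting, and the documents do not support them.

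- *The trial sets out to refute the effect.* The relevant sentence says that current knowledge "requires further studies to substantiate or refute effects that have already been established". It describes what the field needs. The aim stated just before it is to determine effects and make recommendations, and nowhere is p>0.05 said to refute anything.
- *A null result at this size tells us nothing.* An unadjusted interval centred on zero with half-width 0.78 SD excludes benefits above 0.78 SD, so it excludes 0.8 if the synopsis effect size is a standardised mean difference.
- *Harm would often be reported as benefit.* That needs both a substantial true harm, for which the documents give no figure, and a report that ignores the sign of the difference.

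It is also fair to say that the widths and powers rest on a correlation that the documents do not give, which is why they are shown as ranges.

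**Conclusion.** The point holds as a gap in the decision rule. Section 11.4.2 does not identify the effect that answers section 11.1 at the endpoint declared in section 5.1, and it provides no estimate or interval from which a non-significant result could be read.

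For a 0.8 SD difference confined to Day 4, the unspecified choice of effect moves power from 0.12–0.15 (main effect) to 0.42–0.79 (interaction). The contrast that matches the endpoint has 0.57–0.81, at least as high as the interaction at each of the three correlations. Intervals at Day 4 would still be wide, at about ±0.55 to ±0.78 SD. An inconclusive result is therefore a realistic outcome that the plan should be able to express.

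These sizes assume 14 completers per group, correlations of 0.3 to 0.7, equal variances with sphericity, and no multiplicity correction. The mismatch between hypotheses, endpoint and test depends on none of these. This is a cheap improvement, not a flaw that invalidates the trial.

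**What to change.** In section 11.4.2, for each outcome measured at baseline and Day 4 in both arms (physical function, joint circumference, range of motion, skin temperature, pain, 10-metre walk, Timed-Up-and-Go), make the deciding result the device-minus-control difference at Day 4, adjusted for the baseline value, with its two-sided 95% interval. State how it will be read:

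- benefit, only if the interval lies wholly on the benefit side;
- worsening, if it lies wholly on the other side;
- otherwise inconclusive, except for the effect sizes that the interval excludes.

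Restate the hypotheses in section 11.1 as two-sided to match, and keep the repeated-measures model as a supportive analysis. If the synopsis's Bonferroni correction is meant to apply, state the number of comparisons and set the interval level accordingly.

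The baseline-adjusted contrast does not fit three outcomes. Satisfaction is asked only in the device group, and morphine count and length of stay have no baseline. They need their own statement of analysis.

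The cost is a change of wording in sections 11.1 and 11.4.2 and in the synopsis, with no new patients, visits or measurements. The downside is a more cautious conclusion when the interval is wide.

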#### Morphine consumption [number]

H0: The intake of morphine is not reduced by cryotherapy with intermittent dynamic compression compared to control groups during hospitalization.

H1: The intake of morphine is reduced by cryotherapy with intermittent dynamic compression compared to the control group during a hospital stay.

#### Visual analog scale [cm]

H0: The sensation of pain with the Visual Analog scale is not reduced by cryotherapy with intermittent dynamic compression compared to the control group during a hospital stay.

H1: The sensation of pain with the Visual analog scale is reduced by cryotherapy with intermittent dynamic compression compared to the control group during a hospital stay.

#### 10-meter walk test [sec]

H0: The 10-metre gait test is not reduced by cryotherapy with intermittent dynamic compression compared to control groups during a hospital stay.

H1: The 10-metre gait test is reduced by cryotherapy with intermittent dynamic compression compared to the control group during a hospital stay.

#### Timed-Up-and-Go [sec]

H0: The timed up-and-go is not reduced by cryotherapy with intermittent dynamic compression compared to control groups during a hospital stay.

H1: The timed-up-and-go is reduced by cryotherapy with intermittent dynamic compression compared to control groups during a hospital stay.

[figure not shown]
#### Length of stay [days]

H0: The length of stay in hospital is not shortened by cryotherapy with intermittent dynamic compression compared to control groups during a hospital stay. H1: The length of stay in hospital is shortened by cryotherapy with intermittent dynamic compression compared to control groups during a hospital stay.

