### 4.2 Primary Objective

In this project, the effect of postoperative cooling on physiological parameters is measured and compared with the control group.

- Physical Function [Score]
- Patient satisfaction [cm]
- Joint circumference [mm]
- Range of motion [degrees]
- Skin temperature [°C]
- Morphine consumption [number]
- Visual analog scale [cm]
- Length of stay [days]
- 10-meter walk test [sec]
- Timed-Up-and-Go [sec]

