## 5. CLINICAL INVESTIGATION OUTCOMES

### 5.1 Primary Outcome

This study aims to investigate the effects of cryotherapy with intermittent dynamic compression with Game Ready during a hospital stay. The preoperative measurement is the baseline, the 4th postoperative day is the primary endpoint and the measurement 6 weeks postoperative is declared as follow-up. The following parameters are examined for this purpose:

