#### **Length of stay [days]**

The number of hospitalisation days (from admission to and with discharge) is counted and documented.

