In addition to standard physiotherapy (see Chapter 8.1.2 for more information), the subjects in the intervention group will receive the following intervention (according to the manufacturer's protocol for patients with total knee endoprosthesis): 48 hours after the operation, the intervention starts, if tolerable, with little compression (level 1 = 5-15 mmHg) and cooling at the coldest level tolerable by the participant (corresponds to program 2). The cooling should be perceived as "pleasant" by the participant. The intervention lasts one hour, of which 30 minutes are on and 30 minutes off cycles. The on cycle includes the duration of the intervention (cooling and compression), while the off cycles include the rest period. After 60 minutes, the device is removed. If compression is not tolerated, it can also be omitted on the first postoperative day (corresponds to program 1). The intervention is performed twice a day for the first four days after surgery. The coldest tolerable temperature level is to be determined anew for each treatment. The compression level may be increased, although medium compression may only be applied from the second day onwards (corresponds to program 3).

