
Visit 1: Screening and baseline preoperatively: information, written consent, examination of /Exclusion criteria, health questionnaire
 
Physical Function [Score]
 
Joint circumference [mm]
 
Range of motion [degrees]
 
Skin temperature [°C]
 
Visual Analog Pain Scale [cm]
 
10-meter walk test [sec]
 
Timed-up-and-Go [sec]
	60 min

Daily cooling intervention
 
In addition to the usual physiotherapeutic treatment: Daily Cooling and compression. One detailed treatment description can be found in chap. 8.1.1.
	
2x daily one treatment of 60 min = 120 min per day
 
4x 120 min per day = 480 min per stay

Visit 2: Follow up 4th postoperative day
 
Physical Function [Score]
 
Joint circumference [mm]
 
Range of motion [degrees]
 
Skin temperature [°C]
 
Visual Analog Pain Scale [cm]
 
Patient satisfaction [cm]
 
10-meter walk test [sec]
 
Timed-up-and-Go [sec]
	30 min

Visit 3: Follow up 6 weeks postoperatively  Physical Function [Score] Joint circumference [mm] Range of motion [degrees] Skin temperature [°C] Visual Analog Pain Scale [cm] 10-meter walk test [sec] Timed-up-and-Go [sec] Length of stay [days] Morphine consumption [number]	40 min
Total time commitment:	610 min

Any adverse events must be recorded during each visit. These possible time expenditures are not included in the test protocol.

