### **9.3 Procedures at each visit**

All rounds take place on the premises of the Regional Hospital Surselva AG.

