## 11.3 Statistical criteria of termination of the investigation

Only data from subjects who have completed the entire protocol will be included in the study. This ensures that all data has been collected under the same conditions and thus remains homogeneous and comparable.

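### Restricting the analysis to completers can drop patients discharged before Day 4 and so shrink the length-of-stay difference, which is a primary outcome

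*Combined protocol and SAP*

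**What the plan says.** **The outcome.** Section 4.2 lists length of stay among ten primary outcomes, and section 5.2 names no secondary ones. Its definition in section 5.1 is: "The number of hospitalisation days (from admission to and with discharge) is counted and documented". The hypothesis in section 11.1 is one of shortening: "H1: The length of stay in hospital is shortened by cryotherapy with intermittent dynamic compression compared to control groups during a hospital stay".

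**The timetable.** For the study as a whole, section 5.1 states that "the 4th postoperative day is the primary endpoint", and the test log in section 9.1 gives both arms that visit. Section 9.3 adds: "All rounds take place on the premises of the Regional Hospital Surselva AG". For the device arm, section 8.1.1 sets the start at 48 hours after the operation and then says: "The intervention is performed twice a day for the first four days after surgery". The time budget in section 9.1 is "4x 120 min per day = 480 min per stay".

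**The analysis set.** Section 11.3 says: "Only data from subjects who have completed the entire protocol will be included in the study". Section 11.4.1 leaves out partial data sets. Section 11.5 keeps the data of non-completers on file but out of the final analysis. Section 7.4 points the other way for revoked consent: data already collected must be evaluated.

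**What is not said.** No section covers discharge before Day 4, measurement after an early discharge, the number of sessions that counts as completion, or a separate analysis set for length of stay.

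**The concern.** Whether a patient is analysed depends on something that happens after randomisation and is tied to the outcome itself. A patient who leaves hospital on Day 3 and does not come back on Day 4 has an incomplete data set and is dropped, although the length of stay is known exactly. If the device shortens stay, such patients are more frequent in the device arm, so the short stays that the hypothesis predicts are removed from that arm in particular. Randomisation no longer protects the comparison, and the difference is pulled towards zero.

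With 14 patients per arm, a few selective losses matter. A null result could not be read as showing that the device leaves length of stay unchanged. Deletion is also unnecessary for this outcome, because counting hospital days requires no attendance on Day 4.

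**Working it through.** **1. The plan's own figures.** The 480 minutes reproduce as 4 × 120. The total of 28 also reproduces if the effect size of 0.8 is the multivariate f(V) for a group-by-time test with 2 groups and 3 time points. At N = 28 the noncentrality is 0.8² × 28 = 17.92, with df 2 and 25, and power is 0.955. That reading is inferred, since Figure 4 is not shown. Length of stay has one value per patient, so this calculation does not cover it. A two-sided two-sample t-test with 14 per arm and a standardised difference of 0.8 has power 0.53, before any deletion.

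**2. Where the cut-off falls.** The visit sets it at Day 4 in both arms. For sessions it is unclear. A start at 48 hours with sessions through Day 4 covers Days 2, 3 and 4, which is 3 × 120 = 360 minutes. The budget of 480 minutes needs 480 / 120 = 4 days, which would run to about Day 5. The calculation below uses Day 4.

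**3. Assumptions for the size.** None of these come from the documents. The postoperative discharge day K is a normal variable with SD 1.5, rounded to whole days and no lower than 2. Its underlying mean is m in the control arm and m − 1 in the device arm. Counting from admission adds pre-operative days, which have the same expectation in both arms and cancel from the difference.

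**4. Formulas.**
- P(K = k) = Φ((k + 0.5 − m)/1.5) − Φ((k − 0.5 − m)/1.5), with all mass below 2 placed at 2.
- Share discharged before Day 4 = Φ((3.5 − m)/1.5).
- Kept mean = Σ k·P(K = k) / Σ P(K = k), summed over k ≥ 4.

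Example, m = 5: control loses Φ(−1.00) = 0.159 and device loses Φ(−0.33) = 0.369, or 14 × 0.159 = 2.2 and 14 × 0.369 = 5.2 patients. The full means are 5.01 and 4.06 (true difference 0.95). The kept means are 5.447 and 4.931 (difference 0.52).

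**5. Results** (days of shortening; losses are control / device).

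| Control mean | Lost before Day 4 | True | Deleted in both arms | Deleted in device arm only |
|---|---|---|---|---|
| Day 4.5 | 25% / 50% | 0.91 | 5.165 − 4.741 = 0.42 | 4.527 − 4.741 = −0.21 |
| Day 5 | 16% / 37% | 0.95 | 5.447 − 4.931 = 0.52 | 5.011 − 4.931 = 0.08 |
| Day 6 | 5% / 16% | 0.99 | 6.162 − 5.447 = 0.72 | 6.001 − 5.447 = 0.55 |
| Day 7 | 1% / 5% | 1.00 | 7.041 − 6.162 = 0.88 | 7.000 − 6.162 = 0.84 |

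These are exact sums; simulation agrees to within 0.01. In the last column the control arm keeps everyone, so the loss percentages apply to the device arm only. That column needs a stricter reading of completion, discussed under the objection. With deletion in both arms the difference shrinks in every row and never changes sign.

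**The case against.** The strongest defence is that the plan hides nothing. Every stay is to be counted, section 11.5 retains the data of those who drop out, and a shortening that stays above Day 4 remains visible. All of that stands. A reader might infer that shortened stays cannot be observed at all. The documents do not support this: the stays are recorded and then left out of the analysis.

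A reader might also infer that early discharges are deleted in the device arm alone, because a control patient can return on Day 4 whereas a device patient has missed sessions. That is one possible reading. Completion is not defined by session count. Section 11.4.1 speaks of data sets, section 4.1 describes the daily sessions as a maximum, and section 5.4 treats stopping the application separately from leaving the study. In favour of the stricter reading, patient satisfaction is scored after each session and so exists only in the device arm, and the minutes are budgeted per stay. The text does not settle the matter, so the reversed sign in the table cannot be presented as the expected consequence.

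Nor does any section say that discharge is delayed so that sessions can be finished. A floor on stay from that source is conjecture. Counting from admission may add noise, but it does not bias a randomised comparison.

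Finally, the size is not documented. If nearly all patients at this hospital leave well after Day 4, the problem is close to negligible. That stands too, but the plan gives no figure showing that this is so.

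**Conclusion.** The point holds as a risk of attenuation. It rests on three stated features: a primary hypothesis of shorter stay, a protocol with a Day-4 hospital visit and per-stay sessions, and an analysis limited to those who completed everything. It also rests on the silence about discharge before Day 4, and on early-discharged patients not being measured on that day.

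Under the assumed distribution (SD 1.5, benefit about 1 day), deletion in both arms removes more than half of the true difference at a control mean of Day 4.5, just under half at Day 5, about a quarter at Day 6 and about an eighth at Day 7. Deletion in the device arm only would do more damage, and at Day 4.5 would reverse the sign, but this depends on a definition of completion that the plan does not give. If finishing 480 minutes from a 48-hour start were required, the device cut-off would move to about Day 5 and the bias would be larger.

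The change is worth making before data are analysed, because it costs little and the size of the bias cannot be bounded from the documents.

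**What to change.** - **Sections 11.3, 11.4.1 and 11.5:** analyse length of stay in all randomised patients in their allocated arm, whatever sessions or visits they completed. Section 9.1 lists the item under the 6-week visit, so state that it is recorded at discharge and does not depend on attending that visit.
- **Define completeness** for the other outcomes by outcome data and not by sessions received. Leave patient satisfaction out of that definition, since only one arm provides it.
- **Sections 5.1 and 9.1:** state that Day-4 measurements may be taken at a return visit when the patient has already been discharged.
- **Reconcile** the 48-hour start and the four-day schedule in section 8.1.1 with the 480 minutes in section 9.1, and the rule on collected data in section 7.4 with sections 11.3, 11.4.1 and 11.5.

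The outcome itself need not be redefined. A fit-for-discharge date would replace an objective count with a judgement by a treating team that section 6.2.2 does not describe as blinded.

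The cost is a few sentences in the plan and a return trip on Day 4 for the few patients discharged early.
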